6.2 Efficacy Population

The efficacy population will be based on subjects included in the safety population, were randomized, and have at least 4 post-baseline daily scores for the NRS assessment score assessing average pain intensity in the past 24 hours or at least one post-baseline visit (Week 2, Week 4, or Early Termination).

Subjects will be excluded from the efficacy population in the event a subject is given study drug by mistake without being randomized. This will also be classified as a major protocol violation.

Subjects in the efficacy population will be analyzed based on the planned treatment they were randomized to in the study. The efficacy population will be the primary analysis population used for this study.

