12.4 Analysis Populations

Safety analyses will be based on the Safety Population, which is defined as all subjects who receive at least 1 dose of investigational product.

Efficacy analyses will be based on the modified Intent-to-Treat Population, which is defined as all subjects in the Safety Population with at least 1 post baseline assessment of the pain intensity NRS.

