4.7 Analyses Changes from the Protocol

In Section 9.2.5 of the protocol, 'moderate cases' (scores 11-15), and 'severe cases' (scores 16 or higher) were categories defined for Hospital Anxiety and Depression Scale (HADS) based on Zigmond 1983^[22]. However, more recent ranges are defined as 'moderate cases' (scores 11-14), and 'severe cases' (scores 15 or higher) based on Snaith 1994^[21].

In Section 12.4 of the protocol, it mentions that the modified Intent-to-Treat Population will be used for the efficacy analyses. This will be replaced with the Efficacy Population.

In Section 12.5 of the protocol, it mentions that treatment groups 200 mg combined with 50 mg of NYX-2925 will be provided in the summary tables. This specific grouping of multiple treatments will not be performed in this planned statistical analysis.

In Section 12.6.1.1 of the protocol, it states that study site will be used as a fixed factor in the analysis of covariance. Study site will not be included in the any statistical models due to low enrolling sites. Some study sites will not have all four treatment arms assigned to randomized subjects and this can affect some statistical models. The rest of the analyses stated in the protocol support the analyses planned in this SAP.

Section 12.8 of the protocol mentioned that a potential interim analysis would be conducted, but after additional consideration no formal interim analyses will actually be performed for this study. The sample size was calculated using a 0.048 Type I error, but the same results were based on a 0.05 Type I error without having an interim analysis.

5. General Statistical Principles

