6.1 Safety Population

All subjects who were dispensed study drug during the baseline visit and did not return all the study drug in their next visit will be in the safety population. It will be assumed that these subjects in the

safety population have taken at least one dose of study drug. Study drug is not referring to rescue medication that was dispensed at screening or at any other visits.

Subjects in the safety population will be used for all analyses of safety data and will be analyzed based on the actual treatment received in the study. In the event subjects received study drug with multiple study drug treatments by mistake in the study, the following analyses will be updated:

- Latest Treatment and Lowest NYX-2925 Dose Given:
 - o If 10 mg was the lowest NYX-2925 dose given, then that will be used for the remainder of the study after that study drug has been dispensed.
 - o If 50 mg was the lowest NYX-2925 dose given, then that will be used for the remainder of the study after that study drug has been dispensed.
 - o If 200 mg or placebo was given, then NYX-2925 200 mg will be used for the remainder of the study after that study drug has been dispensed.
 - This method will be applied to data regarding: adverse events, concomitant medications, study drug accountability, study drug exposure, and rescue medication.
 - o For example, if a subject received placebo for weeks 1-2 and then received a kit for NYX-2925 50 mg, then 2 different safety treatment arms would be assigned for this subject. Safety data mentioned above in weeks 1-2 would be counted in the placebo group and any time after receiving NYX-2925 50 mg will be counted in the NYX-2925 50 mg group.
- Lowest NYX-2925 Treatment:
 - o Placebo will not be used.
 - Each subject will only be counted in one NYX-2925 treatment group (10 mg, 50 mg, or 200 mg).
 - This method will be applied to all safety data not mentioned above (i.e. clinical laboratory tests, vital sign measurements, electrocardiogram, physical examinations, etc.).

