9.1.3 Primary Efficacy Endpoint Sensitivity Analyses

Missing values that occurred between Study Day 1 through Day 28 for individual NRS scores assessing average pain intensity in the past 24 hours will be imputed in sensitivity analysis. Any missing data for individual scores not collected at Baseline (Study Day -7 through Day -1) will not be imputed. The following 3 imputation methods will be applied:

- Method 1^[10]: Model-Based using SAS® procedures PROC MI and PROC MIANALYZE
 - o Individual missing scores will imputed 5 times^[11] with a random seed number of 8743216514.
 - The Markov chain Monte Carlo method will be used to compute full imputations using the following variables: planned treatment arm and scores at Study Day 1 through Day 28.

- Method 2^[4]: Last Observation Carried Forward (LOCF)
 - Individual missing scores will use the last individual study day value that was collected and will continue to carry that forward until an observed score was collected
 - If Day 1 is missing, then the mean baseline value will be used (not just the Study Day -1 score).
- Method 3^[4]: Baseline Observation Carried Forward (BOCF)
 - o Individual missing scores will use the mean baseline value calculated.

Once the missing data has been imputed based on one of the following methods, the post-baseline analysis visits will be recalculated if they could not be calculated before. For example, if a subject has observed scores collected for Days 22, 23, 24, and 25 then the observed Week 4 analysis visit mean was already calculated. As a result, imputed Days 26, 27, and 28 will not be used in calculation for the Week 4 analysis visit.

No descriptive statistics tables will be created for any of these imputation methods. The mean change from baseline results in Methods 2 (LOCF) and 3 (BOCF) will be summarized with the same ANCOVA model stated in Section 9.1.2.

The mean change from baseline results in Method 1 (Model-Based) will be summarized into 5 individual ANCOVA models stated in Section 9.1.2 based on the imputation number. From there the ANCOVA statistics will be analyzed in PROC MIANALYZE to produce overall statistics for:

- n =the number of records for that treatment or pooled treatment group
- Least Squares Mean for the treatment groups
- Standard Error for the treatment groups
- Least Squares Mean Difference for the NYX-2925 treatment groups versus Placebo
- Standard Error Difference for the treatment groups versus Placebo

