9.3.2 Responder Status Endpoints

Different efficacy responder statuses will be defined based on the following methods [4, 10]:

- Responder at $\geq 30\%$ Pain Reduction:
 - Subjects achieving ≥30% pain reduction on the mean NRS score assessing average pain intensity in the past 24 hours from baseline to Week 4 analysis visit and the subjects must complete the study. Subjects who do not have an analysis visit Week 4 mean NRS score assessing average pain intensity in the past 24 hours will be set to a non-responder.

- Responder at ≥50% Pain Reduction:
 - Subjects achieving ≥50% pain reduction on the mean NRS score assessing average pain intensity in the past 24 hours from baseline to Week 4 analysis visit and the subjects must complete the study. Subjects who do not have an analysis visit Week 4 mean NRS score assessing average pain intensity in the past 24 hours will be set to a non-responder.
- Responder at ≥30% Pain Reduction and Week 4 PGI-C Improved Score:
 - Subjects achieving ≥30% pain reduction on the mean NRS score assessing average pain intensity in the past 24 hours from baseline to Week 4 analysis visit and the subjects must complete the study. Subjects who do not have an analysis visit Week 4 mean NRS score assessing average pain intensity in the past 24 hours will be set to a non-responder.
 - o In addition, to be classified as "responders" subjects must have an analysis visit Week 4 PGI-C score of 1 (Very Much Improved) or 2 (Much Improved). Otherwise, those subjects will be set to non-responders.

The percent change from baseline that is \leq -30.0% is equivalent to \geq 30% pain reduction. Subjects with a calculated mean NRS score assessing average pain intensity in the past 24 hours at analysis visit Week 4 will be provided in a figure based on their percent change from baseline values. The horizontal axis displays a range of percentage-reductions from baseline at Week 4 in the mean NRS score assessing average pain intensity in the past 24 hours and the vertical axis displays the percentage of subjects achieving each of those levels of improvement. The horizontal axis will range from 0% to 100% in percentage-reductions and will not plot subjects with percentages below 0% (i.e. subjects that showed worse pain at Week 4 and the percentage change from baseline \geq 0%).

Frequency distributions, odds ratio, and relative risk analyses described in Section 5.3.5.5 will be used to summarize the responder status endpoints.

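### Responder, PGI-C and BOCF analyses leave out subjects dispensed drug who have fewer than four diary scores and no post-baseline visit, though their own missing-data rules would count them as failures or zero change

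*SAP*

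**What the plan says.** Protocol 12.4 bases efficacy on a modified intent-to-treat set: "all subjects in the Safety Population with at least 1 post baseline assessment of the pain intensity NRS". SAP 4.7 says of that set: "This will be replaced with the Efficacy Population". It gives no reason, although the same section does give one for dropping study site from the models.

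SAP 6.2 requires Safety Population membership, randomisation, and one of two things. The first route is diary data: subjects must "have at least 4 post-baseline daily scores for the NRS assessment score assessing average pain intensity in the past 24 hours". The second route is attendance at any one of three scheduled or early-exit visits after baseline (Week 2, Week 4, Early Termination). The section adds: "The efficacy population will be the primary analysis population used for this study".

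Safety Population membership is inferred from drug returns. Under SAP 6.1, subjects who were dispensed drug at baseline and "did not return all the study drug in their next visit will be in the safety population", with at least one dose then assumed. SAP 5.1.1 confirms that the first dosing date is not collected.

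Three analyses say what to do when the outcome is absent:
- Responder status (SAP 9.3.2): "Subjects who do not have an analysis visit Week 4 mean NRS score" are set to non-responder.
- PGI-C improved (SAP 9.2.4): a missing rating is placed in the not-improved category.
- BOCF (SAP 9.1.3): "Individual missing scores will use the mean baseline value calculated", for Days 1 to 28.

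The table list in SAP 13 assigns all of these to the Efficacy Population: 14.2.1.4.1 (responder), 14.2.4.1 and 14.2.4.2 (PGI-C) and 14.2.1.2.4 (BOCF).

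**The concern.** A rule that counts a missing outcome as failure, or returns it to baseline, is meant to make early loss count against the arm in which it occurs. None of the three rules needs post-baseline data. The baseline pain mean is available too, because SAP 9.1 makes at least 6 baseline diary scores a condition of randomisation. The population filter acts first, however. A subject who takes the drug home and is lost within days, with too few scores and no visit, is removed before the rule can apply.

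At stake are the response rates in each arm and, if such losses are uneven across 10 mg, 50 mg, 200 mg and placebo, the comparisons between arms. Uneven loss is possible: Protocol 7.4 lists adverse events and lack of efficacy among the reasons for withdrawal.

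**Working it through.** **Design inputs.** SAP 4.4 gives 75 per arm, difference 1.05, SD 2.25, 2-sided alpha 0.05 and about 80% power. A noncentral-t calculation gives 81.0% (80.6% at the protocol's 0.048), so the stated figure reproduces. It does not depend on the population rule; it only supplies the 75 per arm used below.

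**Who is in and who is out**, among randomised subjects treated as dosed:

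| Post-baseline data | Protocol mITT | SAP Efficacy Population |
|---|---|---|
| 4 or more scores | in | in |
| 1–3 scores, with a listed visit | in | in |
| 1–3 scores, no listed visit | in | out |
| 0 scores, with a listed visit | out | in |
| 0 scores, no listed visit | out | out |

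The SAP set is thus narrower than the protocol's in one row, wider in another, and the same for subjects with neither scores nor a visit. One detail is open. SAP 5.1.4 takes post-baseline as after Day 1 unless otherwise specified, while the Week 1 diary window in 5.4.2 starts on Day 1, so it is unclear whether a Day 1 score counts toward the four.

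**Primary analysis.** SAP 9.1 needs at least 4 scores within Days 22–28 for a Week 4 mean. A subject with fewer than 4 scores in total cannot have one, so the observed-data ANCOVA is the same with or without these subjects.

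**Responder rate.** The documents give no exclusion count and no expected response rate, so the number excluded k and the true rate r are assumptions. Excluded subjects are all non-responders under 9.3.2. The numerator 75r stays and the denominator falls to 75 − k:

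overstatement = 75r/(75 − k) − r = rk/(75 − k)

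| True rate r | k = 1 | k = 4 |
|---|---|---|
| 30% | 0.30 × 1/74 = 0.41 points | 0.30 × 4/71 = 1.69 points |
| 40% | 0.54 | 2.25 |
| 50% | 0.68 | 2.82 |

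The same formula applies to the PGI-C improved rate.

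**Arm difference.** If all exclusions fall in one arm, the difference shifts by the amounts above. For example, with 25/75 responders in each arm and 3 excluded from active only, 25/72 − 25/75 = 34.7% − 33.3% = 1.4 points. With equal k and equal response there is no spurious difference. With equal k and unequal response, the existing difference is multiplied by 75/(75 − k), which is 1.056 at k = 4.

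**BOCF.** A restored subject with no scores in Days 22–28 has a change of 0, so the arm mean is multiplied by (75 − k)/75: 0.987 at k = 1 and 71/75 = 0.947 at k = 4. If the retained subjects' mean change is −2.0 (assumed), the mean is overstated by 2.0 × k/75, or 0.03 and 0.11 NRS points. With equal k in both arms, a BOCF difference of 1.05 would become 1.04 or 0.99.

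**The case against.** The strongest reply is that the visit route already handles most early leavers. Protocol 7.4 says subjects who terminate early should come back for the Early Termination visit, and footnote c to the Schedule of Procedures gives them the Week 4 procedures. A subject who stops on Day 2 and attends that visit stays in the Efficacy Population and counts as a non-responder. This stands: a reader might infer that the plan discards early dropouts in general, and it does not.

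A reader might also infer that the SAP simply tightened the protocol's set. That is not supported either. The visit route adds subjects with no scores whom the protocol would exclude, the replacement is disclosed, and the net change is unknown.

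Nor is dosing certain for the omitted subjects. SAP 6.1 looks at returns at the next visit and does not say what happens when there is none. Any set built on it still uses information collected after randomisation. This also stands, and the fix has to address it.

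Two further points limit the importance. SAP 6 promises a listing and tables of exclusions with reasons, so a reader could rebuild the responder denominators. The NRS responder endpoints are exploratory, BOCF is one of three imputation sensitivity analyses, and PGI-C is one of many secondary endpoints. The shifts are also small beside sampling error: with 75 per arm, the standard error of a difference at 40% response is √(2 × 0.4 × 0.6/75) = 8.0 points.

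What remains is that tabulating exclusions does not return these subjects to the planned analyses, whose own rules already say how to count them.

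**Conclusion.** The point holds as a minor inconsistency. Three analyses whose missing-data rules need no post-baseline data are run on a population that requires some. Subjects with zero to three scores and no Week 2, Week 4 or Early Termination visit are dropped rather than counted as failures or zero change.

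Within an arm the direction is known. The responder rate can only rise (provided the arm has any responders), and the BOCF mean moves away from zero for subjects with no scores in Days 22–28. The size is not known. The range of 0.4 to 2.8 points rests on assumed exclusions of 1 to 4 of 75 and assumed rates of 30% to 50%, and the true number is probably small. A spurious contrast between arms needs exclusions that differ by arm, and nothing in the documents shows that they will.

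A reader might go further and conclude that the primary result is biased by this rule. It is not: these subjects cannot have a Week 4 mean under either definition.

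**What to change.** Run the responder, PGI-C responder and BOCF analyses on all randomised subjects who were dispensed study drug, by randomised arm. Exclude only those documented as having returned all drug untaken, and treat subjects with no return visit as included. Report the number added per arm beside each table. State in SAP 6.2 whether a Day 1 score counts toward the four, and give the reason for replacing the protocol's population. Settle this before database lock, when SAP 4.6 says the plan becomes final.

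The cost is SAP wording and one population flag, with no new data and no change to the primary analysis. The downside is a few more subjects counted as failures, some with dosing only presumed. The set still depends on drug-return information, so it should not be described as free of post-randomisation criteria.

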6.3 PP Population

The Per Protocol (PP) population will be based on all subjects in the efficacy population and the following criteria:

- Subjects received the same study drug throughout the duration of the study;
- Subjects received the same study drug to which they were randomized;
- Subjects met the randomization inclusion criteria described in Section 7.1 of the protocol;
- Subjects did not use any of the prohibited concomitant medications listed in Section 8.7 of the protocol;
- Subjects who have an overall study drug treatment compliance between 80% and 125%;
- Subjects have an observed mean NRS score assessing average pain intensity in the past 24 hours calculated within the Week 4 efficacy analysis visit window.

Subjects in the PP population will be defined based on a review of the relevant data by the Sponsor prior to database lock. However, subjects dispensed the wrong treatment arm (i.e., a treatment arm other than the one they were randomized to) will be removed from the PP population. Subjects in the PP population will be analyzed based on the planned treatment they were randomized to in the study.

7. Disposition, Baseline, and Other Characteristics

7.1 Subject Disposition

All subjects who were screened in the study will be summarized in a frequency distribution table by their following status after the baseline visit where the denominator will be the number of subjects screened:

- Randomized and Treated
- Randomized and Not Treated
- Not Randomized, but Treated
- Not Randomized and Not Treated

Any subjects "Not Randomized and Not Treated" will be subcategorized for the following reasons collected on the CRF: randomization ineligible, does not meet inclusion/exclusion criteria, withdrew consent, adverse event, protocol non-compliance, lost to follow-up, pregnancy, sponsor terminated the study, and other. Some reasons may have more than one reason collected on the CRF. If the subject meets all the criteria, but is ineligible for study drug treatment arm randomization then "randomization ineligible" will be used in the tables and listings. "Other" will be displayed on the tables if collected on the CRF and no other standardized term may be used.

[figure not shown]
In the event for subjects screened more than once for the study, the latest screening data collected will be used for all subject disposition tables and listings if they were randomized and/or given study treatment. Otherwise, the earliest screening data collected will be used for subjects not randomized or given study treatment.

Frequency distributions of the subjects who completed Visit 4 will be summarized. Furthermore, frequency distributions for the subjects who discontinued prematurely will be summarized along with the primary reason for withdrawal or discontinuation collected on the CRF.

The subject disposition listing(s) will include all subjects with the following data: treatment arm, protocol amendment version, date informed consent signed, date of completing Visit 4 or

Biostats

7.2Demographics and Disease History

Demographics and baseline characteristics will be summarized for the safety, efficacy, and PP populations. Descriptive statistics will be calculated for the following continuous demographic and baseline characteristic variables at screening: age, height, weight, and body mass index (BMI). Frequency distributions will be tabulated for the following categorical demographic variables: sex, childbearing potential, race, and ethnicity.

[figure not shown]
Disease history for both DPN – Lower Extremities and Type II Diabetes will be summarized based on the number of years in the demographics and baseline characteristics table. Each disease events will be provided in the medical history subject listing, but not summarized in the medical history table.

The number of years for each disease be calculated as the (number of days from the onset date to the latest signed informed consent date) / 365.25 and is rounded off by one number after the decimal point. For partial dates collected, the imputation history date described in Section 5.5.3 will be used.

[figure not shown]
Subject listings will include the treatment arm, subject's date of birth, and all continuous/categorical variables listed above.

7.3 Subject Inclusion and Exclusion Criteria

Inclusion and exclusion criteria will be provided in a subject listing where each subject number not meeting each criterion will be displayed.

MPB Biostats

In order for a subject to be randomized, the subject's mean NRS score assessing average pain intensity in the past 24 hours and diary compliance will be used to assess the following inclusion criteria for randomization:

Subject listings will include the treatment arm, protocol amendment version(s), was the subject rescreened (yes/no), and inclusion/exclusion criteria numbers not met. Subjects will be given "Screen Fail" as the treatment arm unless the subject was randomized to a study treatment. Any subjects that may have been randomized to a study treatment in error due to failure to pass the inclusion/exclusion criteria will be reported as protocol deviations. The numbers of the inclusion/exclusion criteria not met will list the protocol amendment version number and a brief description of the inclusion/exclusion criteria. Subject's meeting all inclusion/exclusion criteria, at screening but failing the inclusion criteria for randomization will not be given a number. Therefore, only "Randomization Ineligible" will be presented in the subject disposition tables and listings.

